## 7. STUDY ASSESSMENTS AND PROCEDURES (PART A AND PART B)

Before performing any study procedures, all potential participants will sign an informed consent form (ICF) (as detailed in [Section 10.2.6](#)). Participants will undergo study procedures at the time points specified in the SoE ([Table 8](#)). A participant can also be seen for an unscheduled visit at any time during the study. An unscheduled visit may be prompted by reactogenicity issues, illness visit criteria for COVID-19, or new or ongoing AEs. The site also has the discretion to make reminder telephone calls or send text messages to inform the participant about visits, review eDiary requirements, or follow-up on ongoing or outstanding issues.

The study site staff are responsible for ensuring that participants comply with the allowed study visit windows. If a participant misses a visit, every effort should be made to contact the participant and complete a visit within the defined visit window specified in the SoE ([Table 8](#)). If a participant does not complete a visit within the time window, that visit will be classified as a missed visit and the participant will continue with subsequent scheduled study visits. All safety requirements of the missed visit will be captured and included in the subsequent visit.

In accordance with “FDA Guidance on Conduct of Clinical Trials of Medical Products during COVID-19 Public Health Emergency” ([DHHS 2020](#)), investigators may convert study site visits to home visits or telemedicine visits with the approval of the Sponsor. Such action should be taken to protect the safety and well-being of participants and study site staff or to comply with state or municipal mandates.

General considerations for study assessments and procedures include the following:

- Protocol waivers or exemptions are not allowed. The study procedures and their timing must be followed as presented in the SoE ([Table 8](#)). Adherence to the study design requirements is essential and required for study conduct.
- Immediate safety concerns should be discussed with the Sponsor immediately upon occurrence or awareness to determine if the participant should continue participation in the study.
- All screening evaluations must be completed and reviewed to confirm that potential participants meet all eligibility criteria. The investigator will maintain a screening log to record details of all participants screened and to confirm eligibility or record reasons for screening failure, as applicable.
- Procedures conducted as a part of the participant’s routine clinical management and obtained before signing of the ICF may be utilized for screening or baseline purposes provided that the procedures meet the protocol-specified criteria and are performed within the time frame defined in the SoE ([Table 8](#)).

- The Screening Visit and Day 1 visit may be completed on the same day.

### **7.1. Immunogenicity Assessments**

Blood samples for immunogenicity assessments will be collected at the time points indicated in the SoE ([Table 8](#)). The following immunogenicity assessments will be measured:

- Serum bAb level against SARS-CoV-2, as measured by ligand-binding assay specific to the SARS-CoV-2 S protein and the S protein RBD.
- Serum nAb level against SARS-CoV-2, as measured by pseudovirus neutralization assays.
- The above assays will include SARS-CoV-2 variant antigens, pseudotyped virus expressing SARS-CoV-2 S protein, or virus isolates to assess differences in immunologic responses to different SARS-CoV-2 variant S proteins.
- Testing for serologic markers for SARS-CoV-2 infection, as measured by anti-nucleocapsid antibodies detected by immunoassay at study enrollment (Day 1) and scheduled post-baseline time points.

Sample aliquots will be designed to ensure that backup samples are available and that vial volumes are likely to be adequate for future testing needs. The actual time and date of each sample collected will be recorded in the eCRF. Handling and preparation of the samples for analysis, as well as shipping and storage requirements, will be provided in a separate study manual.

Measurement of bAb and nAb levels will be performed in a laboratory designated by the Sponsor.

According to the ICF ([Section 10.2.6](#)), excess serum from immunogenicity testing may be used for future research, which may be performed at the discretion of the Sponsor to further characterize the immune response to SARS-CoV-2, additional assay development, and the immune response across CoVs.

The maximum amount of blood collected from each participant over the duration of the study, including any extra assessments that may be required, will not exceed blood limits specified by local regulations. Repeat or unscheduled samples may be taken for safety reasons or for technical issues with the samples. Further details are provided in both the ICF and Laboratory Reference Manual.

## **7.2. Efficacy Assessments**

Vaccine efficacy will not be formally assessed in this study, but active surveillance for COVID-19 and SARS-CoV-2 infection through monthly contact and scheduled blood collection (see [Table 8](#)) will be performed.

## **7.3. Safety Assessments and Procedures**

Safety assessments will include monitoring and recording of the following for each participant, according to the SoE ([Table 8](#)):

- Solicited local and systemic ARs ([Section 7.4.3](#)) that occur during the 7 days following vaccination (ie, the day of injection and 6 subsequent days). Solicited ARs will be recorded daily using eDiaries ([Section 7.3.1](#)).
- Unsolicited AEs observed or reported during the 28 days following vaccination (ie, the day of injection and 27 subsequent days). Unsolicited AEs are defined in [Section 7.4.1](#).
- MAAEs from vaccination on Day 1 through EoS or withdrawal from the study.
- AESIs from vaccination on Day 1 through EoS or withdrawal from the study.
- AEs leading to withdrawal from Day 1 through EoS
- SAEs from vaccination on Day 1 through EoS or withdrawal from the study.
- Vital sign measurements before and after vaccine administration
- Physical examination findings (if performed)
- Details of all pregnancies in female participants will be collected after the start of study treatment and until the end of their participation in the study ([Section 7.4.6](#)).

The incidence and severity of the above events will be monitored by the blinded study team members ([Section 7.5](#)).

### **7.3.1. Use of Electronic Diaries**

At the time of consent, the participants must confirm they will be willing to complete an eDiary using either an application downloaded to their smartphone or using a device that will be provided at the time of enrollment. Before enrollment on Day 1, the participant will be instructed to download the eDiary application or will be provided an eDiary device to record solicited ARs ([Section 7.4.3](#)) on Day 1.

On Day 1 (vaccination day), participants will be instructed on thermometer usage to measure body temperature, ruler usage to measure injection site erythema and swelling/induration

(hardness), and self-assessment for localized axillary swelling or tenderness on the same side as the injection arm.

On Day 1 (vaccination day), participants will record data into the eDiary starting approximately 30 minutes after the injection under supervision of the study site staff to ensure successful entry of assessments. The study site staff will perform any retraining as necessary. Participants will continue to record data in the eDiary after they leave the study site, preferably in the evening and at the same time each day, on the day of injection and for 6 days following injection.

Participants will record the following data in the eDiary:

- Solicited local and systemic reactogenicity ARs, as defined in [Section 7.4.3](#), that occur on the day of vaccination and during the 7 days after vaccination (ie, the day of injection and 6 subsequent days). Any solicited AR that is ongoing beyond Day 7 will be reported in the eDiary until it has resolved, and not to exceed 28 days after vaccination. Adverse reactions recorded in the eDiary beyond Day 7 should be reviewed by the study site staff either during the next scheduled telephone call or at the next study site visit.
- Daily oral body temperature measurement should be performed at approximately the same time each day using the thermometer provided by the study site. If body temperature is taken more than once in a given day, only the highest temperature reading should be recorded.
- Other measurements, as applicable, for solicited local ARs (injection site erythema and swelling/induration) will be performed using the ruler provided by the study site.
- Any medications taken to treat or prevent pain or fever on Day 1 or for the next 6 days.

The eDiary will be the only source document allowed for solicited systemic or local ARs (including body temperature measurements). Participants will be instructed to complete eDiary entries daily. The participant will have a limited window on the following day to complete assessments for the previous day; quantitative temperature recordings and measurement of any injection site erythema or swelling/induration reported on the following day may be excluded from the analyses of solicited ARs.

Any new safety information reported during safety telephone calls or at site visits (including a solicited AR) that is not already captured in the eDiary will be described in the source documents as a verbally reported event. Any AR reported in this manner must be described as an unsolicited event and therefore entered on the AE eCRF.

Study site staff will review eDiary data with participants during the safety call 7 days after vaccination.

The eDiary will also be used every 2 weeks from Day 36 to Day 162 and from Day 202 to Day 342 to capture the occurrence of MAAEs, AESIs, SAEs, or AEs leading to withdrawal. The eDiary will prompt the participant to complete an eDiary questionnaire that collects the following data:

- Changes in health since last completing the questionnaire or since in contact with the study site
- Known exposure to someone with known COVID-19 or SARS-CoV-2 infection
- Any experience of symptoms of COVID-19
- Any MAAEs, AESIs, or SAEs

If an eDiary record results in identification of relevant safety events according to the study period or of symptoms of COVID-19, a follow-up safety call will be triggered.

Apart from the safety telephone calls described in [Section 7.3.2](#) at Day 8 and every 2 weeks starting from Day 43 to Day 169 and from Day 209 to Day 349, each participant will complete a questionnaire in an eDiary for Day 36 to Day 162 and from Day 202 to Day 342 ([Table 8](#)). The eDiary responses will be reviewed by study site personnel and may result in a follow-up safety call by the site to the participant.

#### **7.3.1.1. Ancillary Supplies for Participant Use**

Study sites will distribute Sponsor-provided oral thermometers and rulers for use by participants to assess body temperature and injection site reactions, respectively, for recording solicited ARs in the eDiaries. Based on availability, smartphone devices may be provided to those participants who do not have their own device to use for eDiary activities.

#### **7.3.2. Safety Telephone Call**

A safety telephone call is a telephone call made to the participant by trained site personnel. This call will follow an approved script, which will facilitate the collection of relevant safety information. There will be a safety telephone call on Day 8 for each participant to discuss their health and review their eDiary. Safety calls by the site to each participant will occur on Day 8 and every 2 weeks from Day 43 to Day 169 and from Day 209 to Day 349 ([Table 8](#)). The participant will be interviewed according to the script about the occurrence of AEs, MAAEs, AESIs, AEs leading to withdrawal, SAEs, concomitant medications associated with those events, and any nonstudy vaccinations temporally associated with these events ([Section 7.4.7](#)). In addition, study personnel will collect information on known participant exposure to someone

with COVID-19 or SARS-CoV-2 infection and on the participant's experience of COVID-19 symptoms. All safety information collected from the telephone call must be documented in the source documents as described by the participant and not documented on the script used for the safety telephone contact. As noted in [Section 7.3.1](#), an unscheduled follow-up safety call may be triggered if an eDiary record results in identification of a relevant safety event.

### **7.3.3. Laboratory Assessments**

No routine safety laboratory assessments are planned for this study.

A point-of-care urine pregnancy test will be performed at Day 1 before vaccination. At any time, a pregnancy test either via blood or point-of-care urine can be performed, at the discretion of the investigator. If postmenopausal status is not documented in a female participant's medical records, an FSH test to confirm may be performed at the Screening Visit, as necessary and at the discretion of the investigator, to confirm postmenopausal status.

### **7.3.4. Vital Sign Measurements**

Vital sign measurements will include systolic and diastolic blood pressure, heart rate, respiratory rate, and body temperature (preferred route is oral). The participant will be seated for at least 5 minutes before all measurements are taken. Vital signs will be measured at the time points indicated in the SoE ([Table 8](#)). Vital signs are to be collected pre- and post-vaccination on the day of injection (Day 1) only. When applicable, vital sign measurements should be performed before blood collection.

Participants who are febrile (body temperature  $\geq 38.0^{\circ}\text{C}/100.4^{\circ}\text{F}$ ) before injection on Day 1 must be rescheduled within the relevant window period to receive the injection. Afebrile participants with minor illnesses may be vaccinated at the discretion of the investigator.

### **7.3.5. Physical Examinations**

A full physical examination, including height and weight, will be performed at Day 1 as indicated in the SoE ([Table 8](#)). The full examination will include assessment of skin, head, ears, eyes, nose, throat, neck, thyroid, lungs, heart, cardiovascular system, abdomen, lymph nodes, and musculoskeletal system and extremities. Any clinically significant finding identified during a study visit should be reported as an MAAE.

Symptom-directed physical examinations may be performed at other time points at the discretion of the investigator. On the day of vaccination, before injection, the arm receiving the injection should be examined and the associated lymph nodes should be evaluated.

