Phase 3 study (mRNA-1273-P301) definition of COVID-19	
The participant must have experienced at least TWO of the following systemic symptoms: Fever (<math>\geq 38^{\circ}\text{C}</math>), chills, myalgia, headache, sore throat, new olfactory and taste disorder(s),
 
OR
 
The participant must have experienced at least ONE of the following respiratory signs/symptoms: cough, shortness of breath or difficulty breathing, OR clinical or radiographical evidence of pneumonia; AND The participant must have at least one NP swab, nasal swab, or saliva sample (or respiratory sample, if hospitalized) positive for SARS-CoV-2 by RT-PCR.

End of Study (EoS)	Completion of the last visit of the last participant in the study or last scheduled procedure, as shown in the schedule of events ( Table 8 ) for the last participant in the study.
Lost to follow-up (LTFU)	A participant who repeatedly fails to return for scheduled visits without stating an intention to withdraw consent and is unable to be contacted by the study site.
MAAE	An AE that leads to an unscheduled visit to a healthcare provider.
Nonchildbearing potential	Surgically sterile (history of bilateral tubal ligation, bilateral oophorectomy, hysterectomy) or postmenopausal (defined as amenorrhea for $\geq 12$ consecutive months prior to screening without an alternative medical cause).
Screen failures	Participants who consent to participate in the clinical study but are not subsequently assigned to treatment.
SAE	
An AE is considered an SAE if, in the view of either the investigator or Sponsor, it results in any of the following outcomes (see Section 7.4.2 for further details of each criterion):
 

• Death

• Is life-threatening

• Inpatient hospitalization or prolongation of existing hospitalization

• Persistent or significant incapacity or substantial disruption of the ability to conduct normal life functions

• Congenital anomaly or birth defect

• Medically important event.

Term/Concept	Definition
Symptomatic COVID-19	The presence of one of the CDC-listed symptoms ( https://www.cdc.gov/coronavirus/2019-ncov/symptoms-testing/symptoms.html ) and a positive RT-PCR test on a respiratory sample.

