**Table 1: Part A Objectives and Endpoints**

Objectives	Endpoints
Primary	

To assess the safety and reactogenicity of the study vaccine candidates

	

Frequency and grade of each solicited local and systemic reactogenicity AR during a 7-day follow-up period after vaccination

Frequency and severity of any unsolicited adverse events (AEs) during the 28-day follow-up period after vaccination

Frequency of any serious AEs (SAEs), medically attended AEs (MAAEs), AEs leading to withdrawal from study participation, and AEs of special interest (AESIs) from Day 1 to end of study (EoS)

To assess the immunogenicity of the study vaccine candidates

	

Immune response of the study vaccine candidates against the ancestral severe acute respiratory syndrome coronavirus 2 (SARS-CoV-2) and against SARS-CoV-2 variants, including B.1.351, at Day 29 by geometric mean titer (GMT), geometric mean fold rise (GMFR), and seroresponse rate (SRR)

To compare the immune response elicited by the mRNA-1283 study vaccine candidates with the immune response elicited by the mRNA-1273 vaccine when administered as a booster at Day 29 by GMT, GMFR, and SRR

Secondary	

To evaluate the immunogenicity at all immunogenicity time points

	

Immune response of the study vaccine candidates against ancestral SARS-CoV-2 and against SARS-CoV-2 variants at all immunogenicity time points by GMT, GMFR, and SRR

Objectives	Endpoints
Exploratory	

 
• To characterize cellular immunogenicity
 
	
 
• Frequency, magnitude, and phenotype of antigen-specific B- and T-cells, to include B-cell and T-cell receptor repertoires
 

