**Table 2: Part B Objectives and Endpoints**

Objectives	Endpoints
Primary	

 
• To assess the safety and reactogenicity of the mRNA-1283.529 booster vaccine candidate
 
	
 
• Frequency and grade of each solicited local and systemic reactogenicity AR during a 7-day follow-up period after vaccination
 
• Frequency and severity of any unsolicited AEs during the 28-day follow-up period after vaccination
 
• Frequency of any SAEs, MAAEs, AEs leading to withdrawal from study participation, and AESIs from Day 1 to EoS
 

 
• To assess the immunogenicity of the mRNA-1283.529 booster vaccine candidate as the second booster dose
 
	
 
• Immune response of the mRNA-1283.529 booster vaccine candidate against SARS-CoV-2 Omicron variant (B.1.1.529) at Day 29 by GMT, GMFR, and SRR
 

Secondary	

Objectives	Endpoints

• To assess the immunogenicity at all immunogenicity time points

	

• Immune response of the mRNA-1283.529 vaccine candidate against the ancestral SARS-CoV-2 and against SARS-CoV-2 variants at all immunogenicity time points by GMT, GMFR, and SRR

• 

Exploratory	

• To characterize cellular immunogenicity

	

• Frequency, magnitude, and phenotype of antigen-specific B- and T-cells, to include B-cell and T-cell receptor repertoires

To conduct active detection of symptomatic and asymptomatic SARS-CoV-2 infection	

• Laboratory-confirmed asymptomatic or symptomatic SARS-CoV-2 infection will be defined in participants:

– Negative SARS-CoV-2 anti-nucleocapsid antibody blood test at Day 1 that becomes positive at Day 29 or later, OR

– Positive SARS-CoV-2 RT-PCR from nasopharyngeal swab

• To evaluate the genetic and/or phenotypic relationships of isolated SARS-CoV-2 strains to the vaccine sequence

	

• Comparison of the SARS-CoV-2 genetic sequence of viral isolates with the vaccine sequence and characterization of immune responses to vaccine breakthrough isolates

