#### **7.4.4. Medically Attended Adverse Events**

An MAAE is an AE that leads to an unscheduled visit to an HCP. This would include visits to a study site for unscheduled assessments (eg, abnormal laboratory follow-up, COVID-19 [Section 7.3.6]) and visits to HCPs external to the study site (eg, urgent care, primary care physician). Investigators will review unsolicited AEs for the occurrence of any MAAEs. Unsolicited AEs will be captured on the AE page of the eCRF.

All confirmed COVID-19 cases will be recorded as MAAEs.

All suspected cases of anaphylaxis should be recorded as MAAEs and reported as an SAE, based on the criteria for a medically important event, unless the event meets other serious criteria. As an SAE, the event should be reported to the Sponsor or designee immediately and in all circumstances within 24 hours per [Section 7.4.11](#). The investigator will submit any updated anaphylaxis case data to the Sponsor within 24 hours of it being available. For reporting purposes, a participant who displays signs or symptoms consistent with anaphylaxis (as follows) should be reported as a potential case of anaphylaxis. This is provided as general guidance for investigators and is based on the Brighton Collaboration case definition ([Rüggeberg et al 2007](#)).

Anaphylaxis is an acute hypersensitivity reaction with multiorgan system involvement that can present as, or rapidly progress to, a severe life-threatening reaction. It may occur following exposure to allergens from a variety of sources.

Anaphylaxis is a clinical syndrome characterized by the following:

- Sudden onset AND
- Rapid progression of signs and symptoms AND
- Involves 2 or more organ systems, as follows:
  - **Skin/mucosal:** urticaria (hives), generalized erythema, angioedema, generalized pruritus with skin rash, generalized prickle sensation, and red and itchy eyes.
  - **Cardiovascular:** measured hypotension, clinical diagnosis of uncompensated shock, loss of consciousness or decreased level of consciousness, and evidence of reduced peripheral circulation.
  - **Respiratory:** bilateral wheeze (bronchospasm), difficulty breathing, stridor, upper airway swelling (lip, tongue, throat, uvula, or larynx), respiratory distress,

persistent dry cough, hoarse voice, sensation of throat closure, sneezing, and rhinorrhea.

- **Gastrointestinal:** diarrhea, abdominal pain, nausea, and vomiting.

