#### **7.4.12. Time Period and Frequency for Collecting AE, AESI, and SAE Information**

Medical occurrences that begin before IP administration but after obtaining informed consent will be recorded in the Medical History/Current Medical Conditions section of the eCRF and not in the AE section; however, if the condition worsens at any time during the study, it will be recorded and reported as an AE.

Adverse events may be collected as follows:

- Observing the participant
- Receiving an unsolicited complaint from the participant
- Questioning the participant in an unbiased and nonleading manner

Solicited AEs will be collected from the day of injection through 6 days after vaccination. Other (unsolicited) AEs will be collected from the day of injection through 28 days after vaccination.

Serious AEs (including AESIs) will be collected from the start of IP administration until the last day of study participation.

All SAEs and AESIs will be recorded and reported to the Sponsor or designee immediately and under no circumstance should this exceed 24 hours of becoming aware of the event via the EDC system. If a site receives a report of a new SAE or AESI from a study participant or receives updated data on a previously reported SAE or AESI and the eCRF has been taken offline, then the site can report this information on a paper SAE or AESI form using the SAE Mailbox, the SAE Hotline, or the SAE Fax line ([Section 7.4.11](#)).

An abnormal value or result from a clinical or laboratory evaluation can also indicate an AE if it is determined by the investigator to be clinically significant (eg, leads to study drug discontinuation or meets any serious criteria). If this is the case, it must be recorded in the source document and as an AE on the appropriate AE form(s). The evaluation that produced the value or result should be repeated until that value or result returns to normal or is stabilized and the participant's safety is not at risk.

Investigators are not obligated to actively seek AEs or SAEs after EoS participation. However, if the investigator learns of any SAE (including a death) at any time after a participant has withdrawn from or completed the study, and the investigator considers the event to be reasonably related to the IP or study participation, the investigator must promptly notify the Sponsor.

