### **6.3.1. Adverse Events**

A treatment-emergent AE (TEAE) is defined as any event not present before exposure to study vaccine or any event already present that worsens after exposure to study vaccine. [Note: worsening of a pre-existing condition after vaccination will be reported as a new AE.]

Adverse events will also be evaluated by the investigator for the coexistence of MAAE which is defined as an AE that leads to an unscheduled visit to a healthcare practitioner. All confirmed COVID-19 cases will be recorded as MAAEs.

AEs of special interest (AESI) are defined in Appendix 4 of the protocol.

Unsolicited AEs will be coded by PT and SOC using the latest MedDRA available at the analyses and summarized by treatment group and follow-up period (defined in [Section 6.1](#)).

All summary tables (except for the overall summary of AEs) for unsolicited AEs will be presented by SOC and PT for TEAEs with counts of subjects included. SOC will be displayed in internationally agreed order. PT will be displayed in descending order of frequency of mRNA-1273 **CCI** and then alphabetically within SOC. When summarizing the number and percentage of subjects with an event, subjects with multiple occurrences of the same AE or a continuing AE will be counted once. Subjects will be presented according to the highest severity in the summaries by severity, if subjects reported multiple events under the same PT.

Percentages will be based upon the number of subjects in the Safety Set within each treatment group.

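### Protocol 7.3.5 and Table 8 footnote 3 allow scheduled-visit findings to be counted as MAAEs without meeting the MAAE definition that underlies a primary safety endpoint

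*Protocol*

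**What the plan says.** The reporting instruction is in Protocol 7.3.5 and is repeated in footnote 3 of the Schedule of Events (Table 8): "Any clinically significant finding identified during a study visit should be reported as an MAAE". It sets no condition about an unscheduled visit.

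The definition appears in three places, and they agree:

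- Protocol 7.4.4: "An MAAE is an AE that leads to an unscheduled visit to an HCP". On visits to the site itself it adds: "This would include visits to a study site for unscheduled assessments".
- Protocol glossary: "An AE that leads to an unscheduled visit to a healthcare provider".
- SAP 6.3.1: "MAAE which is defined as an AE that leads to an unscheduled visit to a healthcare practitioner".

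MAAE frequency from Day 1 to end of study belongs to the primary safety endpoints. For Part A, Table 1 lists "Frequency of any serious AEs (SAEs), medically attended AEs (MAAEs), AEs leading to withdrawal from study participation" together with AESIs. For Part B, Table 2 lists "Frequency of any SAEs, MAAEs, AEs leading to withdrawal from study participation, and AESIs from Day 1 to EoS".

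For findings that predate the injection, Protocol 7.4.12 says: "Medical occurrences that begin before IP administration but after obtaining informed consent will be recorded in the Medical History/Current Medical Conditions section". Protocol 7.3 starts MAAE collection at vaccination.

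**The concern.** One term has two incompatible rules, and it feeds a primary endpoint. A site that follows 7.3.5 reports an MAAE for a finding made at a routine Day 29, Day 181 or Day 366 visit. A site that follows 7.4.4 does not, unless the finding sends the participant to an unscheduled visit. The MAAE percentage would then mix events that prompted unscheduled care with findings that surfaced only because the protocol scheduled a visit, in proportions that depend on which section a site read.

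The conflict matters most late in follow-up. Protocol 7.4.7 and Table 8 collect ordinary unsolicited AEs for 28 days only, while MAAEs run to end of study. At Day 181 and Day 366 the MAAE label can therefore decide whether a finding is collected at all, unless it is an SAE, an AESI or an AE leading to withdrawal.

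**Working it through.** The plan gives no figure to reproduce. The trial tests no formal hypotheses (Protocol 8.2), and no expected MAAE count is stated. The check is a comparison of texts, followed by one line of arithmetic for scale.

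**Step 1: where examinations can occur.** In Table 8 the examination row is marked at Screening, Day 1, Day 29, Day 181, Day 366 and the unscheduled visit. All but the last are scheduled.

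**Step 2: classify the same finding under each rule.**

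| Finding | 7.3.5 and footnote 3, read literally | Glossary, 7.4.4, SAP 6.3.1 | Conflict |
|---|---|---|---|
| Before injection (Screening or Day 1) | MAAE | Medical history (7.4.12) | In wording; see step 4 |
| After injection, at an unscheduled visit that the event prompted | MAAE | MAAE | None |
| After injection, at a scheduled visit, later prompting an unscheduled one | MAAE | MAAE | None |
| After injection, at a scheduled visit within the 28-day window, no unscheduled visit follows | MAAE | AE, not MAAE | Yes |
| After injection, at Day 181 or Day 366, no unscheduled visit follows | MAAE | Not MAAE; outside the 28-day window for ordinary unsolicited AEs | Yes, and capture depends on the label |

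The problem is confined to the last two rows.

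**Step 3: does the analysis remove these events?** SAP 6.3.1.1 and 6.3.1.2 tabulate MAAEs overall and by system organ class and preferred term. Neither includes a derivation that checks for an unscheduled visit. SAP section 7 declares no changes from the protocol's planned analyses.

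**Step 4: do pre-injection findings reach the endpoint?** Most should not:

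- Protocol 7.3 collects MAAEs from vaccination onward.
- Protocol 7.4.12 sends earlier occurrences to medical history.
- Protocol 7.4.10 does not count a condition present at screening as an unsolicited AE unless it deteriorates.
- Protocol 7.4.7 analyses AEs before injection separately.
- SAP 6.3.1 presents its unsolicited-AE tables by class and term for treatment-emergent events.

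The literal clash remains, because the one full examination is on Day 1 and 7.3.5 makes no exception for it.

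**Step 5: scale.** For k participants whose only MAAE is a finding of the last two kinds, in an arm of n, the addition to the arm's percentage is 100 × k/n. With n = 70, the ceiling per arm in Protocol 8.3:

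- k = 0: no change
- k = 1: 100 × 1/70 = 1.4 percentage points
- k = 2: 100 × 2/70 = 2.9 percentage points
- k = 3: 100 × 3/70 = 4.3 percentage points

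The values of k are illustrative assumptions; the documents offer no basis for choosing among them. A participant who already has a qualifying MAAE adds nothing to the percentage.

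**The case against.** **It may be a deliberate capture rule.** Section 7.4.4 already adds events to the MAAE category by instruction: confirmed COVID-19 and suspected anaphylaxis. With ordinary unsolicited AEs closed after 28 days, an MAAE label is a practical way to keep a late finding. This is the strongest point on the other side. But those additions are stated in 7.4.4 itself, and the COVID-19 one is carried into SAP 6.3.1. The examination rule appears in neither. Protocol 7.4.7 also gives another route, placing examination findings classed as AEs on the AE page. If the extension is intended, the definition does not say so.

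**The SAP restates the strict definition.** SAP 6.3.1 has the investigator evaluate AEs for MAAE status, and the SAP introduction says the SAP prevails where its methods differ from the protocol's. That review may filter some events. It does not withdraw the instruction to sites, and the tabulations have no check of their own.

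**Opportunities are few.** Examinations after Day 1 are symptom-directed and discretionary, vital signs are for Day 1 only (Protocol 7.3.4), and no routine safety laboratory tests are planned (Protocol 7.3.3). The sentence also sits under physical examinations, so its natural reach is examination findings. All of this stands and supports a small effect.

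**Stronger readings that a reader might infer.** One is that every finding becomes a false MAAE; findings at or leading to an unscheduled visit qualify properly. Another is that Day 1 pre-injection findings swell the endpoint; step 4 shows that most should drop out. A third is that the rate is materially inflated or unusable beside other MAAE rates. The literal rule can only add events, so any effect on the rate is upward, but no amount can be shown, and neither document plans a comparison with outside rates.

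**Conclusion.** The contradiction is real and stands in current text in two places. Post-injection findings at scheduled visits that lead to no unscheduled visit can be counted in a primary safety endpoint without meeting its definition, and sites can code identical findings differently. This is a minor point: the size is unknown and probably small, at 1.4 percentage points per affected participant in a full arm of 70, if that participant has no other MAAE.

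In Part A one rule applies to all arms and the assessors are blinded, so misclassification should be similar across arms. It then disturbs the level and meaning of the rate more than the contrast. Part B is open-label, so that protection is weaker there.

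The conclusion assumes that sites act on 7.3.5 as written for at least some findings. If all sites apply 7.4.4 instead, the rate is unaffected, but late findings may go unrecorded.

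**What to change.** Reconcile 7.3.5 and Table 8 footnote 3 with the glossary, 7.4.4, 7.4.7, 7.4.12 and SAP 6.3.1, in one of two ways.

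**Keep the definition.** State in both places that:

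- a post-injection finding that is an AE goes on the AE page at any visit through end of study;
- it is flagged as an MAAE only if it meets 7.4.4;
- a pre-injection finding goes to medical history.

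The words about any visit through end of study are needed. Telling sites only to record an AE would leave Day 181 and Day 366 findings without a clear home: 7.4.7 and Table 8 stop ordinary unsolicited collection at 28 days, although 7.4.10 is worded more broadly. Sections 7.4.7 and 7.4.12 and the unsolicited-AE row of Table 8 should carry the same exception.

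**Or widen the definition.** If broad capture is intended, state the extension in 7.4.4 and SAP 6.3.1, with the glossary aligned, and tabulate findings without an unscheduled visit separately from MAAEs that meet the existing definition.

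The cost is a few sentences of text, plus a small amount of extra recording under the first option or one extra table row under the second. No change to design, sample size or analysis model is needed.
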